#### **Serious Adverse Event**

- A Serious Adverse Event (SAE) is an AE occurring during any study phase (eg, run-in, treatment, washout, follow-up), and at any dose of the investigational product, comparator or placebo, that fulfills one or more of the following criteria:

- Results in death
- Is immediately life-threatening
- Requires inpatient hospitalization or prolongation of existing hospitalization
- Results in persistent or significant disability or incapacity
- Is a congenital abnormality or birth defect
- Is an important medical event that may jeopardize the patient or may require medical intervention to prevent one of the outcomes listed above.

Any event or hospitalization that is unequivocally due to progression of disease, as determined by the investigator, must not be reported as an SAE.

The causality of SAEs (their relationship to all study treatment) will be assessed by the investigator(s)

### Reporting of Adverse Events

When recording/reporting AEs, the use of diagnoses is preferred (when possible) to recording/reporting a list of signs and symptoms. However, if a diagnosis is known and there are other signs or symptoms that are not generally part of the diagnosis, the diagnosis and each sign or symptom will be recorded/reported separately.

### Illiterate Subjects

Subjects with all levels of literacy will be eligible for this study. The consent document will be read to those volunteers and the process will be documented in the research file.

Subsequently, the informed consent will be signed by the volunteer making their mark in the signature section in order to document their understanding. A witness will be present to confirm the consent process has taken place. Both the witness and person conducting the consent process will sign and date the consent. The investigator obtaining consent will ask each subject to reiterate what will be required from them, risks and benefits, and their rights as a participant in order to ensure their full understanding of the study.

### Non-English Speaking Subjects

Subjects who do not understand or speak English will also be eligible for this study. The consent form will be read to those non-English speaking study candidates in their primary language by a translator from the University Hospitals of Cleveland translation/International Visitors Center. A witness (who speaks English and the study subject's language) will be present to confirm the consent process has taken place. Both the witness and person conducting the consent process will sign and date the consent. The investigator obtaining consent will ask the study candidate via the translator to reiterate what will be required from him/her, risks and benefits, and his/her rights as a participant in order to ensure their full understanding of the study.

### BENEFITS

There may be no direct benefit to patients from participating in this study. Their participation in the study will allow collection of valuable information about the potential benefits of zinc in persons infected with the HIV virus. This information may be useful to them and other people with HIV disease.

### **ALTERNATIVES**

Alternatives to participation in this study are not to participate and to receive the standard of care from the patient's primary care doctor.

### **COST TO PARTICIPANTS**

There is no cost to participants for the study related clinic visits, examinations or laboratory test required by this study. Medical costs of other treatment or examinations outside of the study will be the responsibility of the patient or their insurance company. Patients will be provided zinc supplements free of charge for the entire duration of the study. The study drug will not be provided after they finish the study (whether they complete the study or prematurely stop study participation).

### **PAYMENT TO SUBJECTS**

For completed study visits screening I subjects will receive a food voucher and either a RTA pass or parking validation. Screening II, week 6 and week 18, patients will receive \$25.00 that day. Entry week 12 and week 24, patients will receive \$50.00 that day (total of \$225 for completing the entire study). This payment will help cover the expense of childcare, transportation and time off work that patients may incur as a result of being in this study. To help with the cost of gas, for participants traveling 20-40 miles one way for their appointments, they will also be given a \$15.00 gas card to cover the cost of the transportation. Participants traveling > 40 miles one way for their appointments will also be given a \$30.00 gas card to cover the cost of transportation. Subjects will be asked to fast (nothing to eat or drink for 8 hours prior to visit) at entry, week 6, week 12, week 18 and week 24, therefore a \$5.00 meal voucher will be provided for subjects to use in the University Hospitals cafeteria. In addition either one all day RTA pass will be provided or a parking voucher to use in designated University Hospitals parking garages will be provided to cover the cost of transportation.

### **RISKS AND DISCOMFORTS:** The risks for taking part in this study are:

Blood Draw: Risks associated with drawing blood include: pain, bleeding, and bruising at the site of the blood draw. Other rare risks include: lightheadedness and/or fainting or infection at the site.

EndoPAT: This is a painless imaging test that has no short or long-term risks. The endoPAT test may be mildly to moderately uncomfortable because of the blood pressure cuff that is applied to the patients' arm tightly.

Fasting: Some individuals find fasting to be bothersome. It may make some individuals feel anxious, irritable, or hungry. Patients who are required to take their morning medications with food should wait until after the visit has been completed to take their medications.

Pregnancy: Zinc may not be safe for unborn babies. If patients are having sex that could lead to pregnancy, they must agree not to become pregnant. Because of the risk involved, patients and their partner must use two methods of birth control that they discuss with the study staff. They must continue to use both methods until 6 weeks after stopping study drug. They may choose two of the birth control methods listed below:

- Birth control drugs that prevent pregnancy given by pills, shots, intra-vaginal ring or placed on or under the skin
- Male or female condoms with or without a cream or gel that kills sperm
- Diaphragm or cervical cap with a cream or gel that kills sperm
- Intrauterine device (IUD)

If women can become pregnant, they must have a pregnancy test before they enter this study. The pregnancy test must be negative. In addition, if study subjects think they may be pregnant at any time during the study, they are to tell the study staff right away. In the event that a patient becomes pregnant while on study, they will be taken off study, and no further evaluations or tests will be performed as part of the study.

Zinc Supplementation: At the doses used, uncommon side effects include nausea, vomiting, and abdominal pain (gastritis). At higher doses and when used for a long periods (years), copper deficiency and related anemia may happen. This is extremely unlikely since we are only giving 90 mg daily for up to 24 weeks. Such doses have been shown to be safe even when given for 12 months to elderly frail subjects. In addition, in diseases such as Wilson's disease, zinc is given at a dose of 50 mg three times daily for prolonged durations. We will closely monitor subjects who will receive blood draws for chemistries, hematology and liver enzymes.

Cognivue test: There are no physical risks associated with completing this computerized questionnaire. The test will take about 10 - 30 minutes to complete during each visit

OTHER RISKS: Patients are informed to tell their study doctor or study nurse about all other drugs they are currently taking including non-prescription medications, alcohol, recreational, and herbal products. These drugs, if taken with the study medication, can result in dangerous interactions. If patients have questions about the drug that will be used in this study and the potential for interaction with other drugs that they take, they are instructed to ask their study doctor to provide additional information.

In addition to the risks and discomforts listed here, there may be others that are currently not known.

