### **TIMING OF EVALUATIONS**

**Screening I/II:** all screening evaluations to determine eligibility must be completed within 30 days prior to study entry.

**Entry:** evaluations must occur within 30 days after screening evaluations. If subject shows up ill with any acute symptom, the visit will be postponed until all symptoms resolved for at least 7 days.

**On-Study Evaluations:** study visits must be scheduled on the weeks indicated in the schedule of events +/- 14 days.

**Premature study discontinuation:** Subjects who stop study will undergo the premature study discontinuation evaluations as outlined in the Schedule of events under Week 24 visit. However if subjects stop study medication at any point during the study they will be asked to remain on study and continue to follow the procedures outlined.

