### **TOXICITY MANAGEMENT**

Only toxicities related to study drugs (zinc) will be considered. Toxicities felt to be unrelated to study drugs will be left to the discretion of the primary care provider of the study participants. AACTG grading system will be used for evaluation for Grading Adult Adverse Experiences.

-Subjects who develop a new Grade 1 adverse event or toxicity may continue study drug without alteration of the dosage. Subjects experiencing Grade 1 adverse event who choose to withdraw from the study should be encouraged to complete the study evaluations as outlined in the Schedule of events.

- For all toxicities of Grade 2 thought to be related to the study drug, the study medication can be held at the discretion of the local investigator. If unable to resume it within 3 weeks, then the subject will be taken off study drugs but will continue to be followed and undergo the evaluations as per schedule of events.

- For all toxicities Grade 3 thought to be related to study drug, study medication will be held until the toxicity grade returns to  $\leq$  Grade 2 or to the entry value. If unable to resume study drugs for longer than 3 weeks, then the subject will be taken off study drugs but will continue to be followed and undergo the evaluations as per schedule of events.

- For any Grade 4 toxicity (confirmed  $\geq$  2 values for laboratory abnormalities) regardless of the cause, subjects will be taken off study drugs but will continue to be followed and undergo the evaluations as per schedule of events. Exceptions are asymptomatic elevation of indirect bilirubin in subjects receiving indinavir or atazanavir therapy, asymptomatic elevation of CPK, or elevations in lipid levels.

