### **CRITERIA FOR PERMANENT STUDY DISCONTINUATION:**

-Request by the subject to withdraw

-At the discretion of the IRB

-Pregnancy or breast-feeding

-Request of the primary care physician if s/he thinks the study is no longer in the best interest of the subject.

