All analysis will be by intent to treat. All subjects, regardless of whether they remain on study drug, will continue to be followed throughout the duration of the study. It is standard practice in the HIV studies where inflammation markers are measured, that every attempt would be made to schedule study visits during a time that subjects are not acutely ill. That would mean that a visit would be rescheduled if a patient shows up sick, as acute illnesses may affect inflammation markers. A period of >7 days ill-free would be required. This happens rarely overall but if it does in the setting of this study, participants would be asked to come back after illness resolves.

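### The pregnancy rule cancels the discontinuation visit that the protocol gives to every subject who stops study, and no active follow-up of pregnancy outcome is described

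*Combined protocol and SAP*

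**What the plan says.** - Risks and Discomforts, Pregnancy paragraph: a participant who conceives on study is handled as follows: "they will be taken off study, and no further evaluations or tests will be performed as part of the study". The paragraph gives the ground for caution, "Zinc may not be safe for unborn babies", and requires contraception until 6 weeks after the last dose.
- Criteria for Permanent Study Discontinuation lists "Pregnancy or breast-feeding". It says nothing about which evaluations are then done.
- Timing of Evaluations, on premature discontinuation: "Subjects who stop study will undergo the premature study discontinuation evaluations as outlined in the Schedule of events under Week 24 visit". No exception for pregnancy is stated.
- Serious Adverse Event, among the criteria: "Is a congenital abnormality or birth defect".
- Intervention and Duration, and Post-study Follow-up and Transition of Care, both end follow-up at week 24.
- The Data Safety and Monitoring Plan and the Adverse Events sections do not say how the outcome of a pregnancy would be sought or recorded.

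**The concern.** Being taken off study is the very event that triggers the discontinuation visit in Timing of Evaluations. The Pregnancy paragraph takes the participant off study and forbids that visit. A coordinator who follows one section breaks the other. If the Pregnancy paragraph prevails, a participant with an exposure that the protocol itself flags as possibly harmful leaves without a closing safety assessment.

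The second part concerns the outcome of the pregnancy. The protocol acknowledges a possible fetal risk and treats a birth defect as serious, but a defect recognised at birth would appear after all follow-up has ended. Unless someone is told to look, it may never reach the trial's safety record.

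**Working it through.** No stated figure in the plan bears on this point, so there is none to reproduce. The check is a comparison of sections, a timing calculation and a rough count.

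**Sections side by side**

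1. Criteria for Permanent Study Discontinuation makes pregnancy a reason to leave the study. The Pregnancy paragraph agrees.
2. Timing of Evaluations says that those who leave the study have the week 24 evaluations. Neither it nor the discontinuation criteria exempts pregnancy.
3. The Pregnancy paragraph says no evaluations or tests follow. Statements 2 and 3 cannot both be carried out for the same participant.

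**Timing of birth against the end of follow-up**

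Inputs from the protocol: a negative pregnancy test within 72 hours before study drug starts, so conception is at about week 0 or later; follow-up ends at week 24; contraception continues for 6 weeks after the last dose. Assumption, not in the documents: term birth comes 38 weeks after conception.

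Week of birth = c + 38, where c is the week of conception. Weeks after follow-up ends = c + 38 − 24.

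- c = 0: birth at week 38; 38 − 24 = 14 weeks after.
- c = 24: birth at week 62; 62 − 24 = 38 weeks after.
- c = 30 (24 + 6, the end of the contraception window): birth at week 68; 68 − 24 = 44 weeks after.

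With 35 to 40 weeks to term instead, on-study conceptions give 0 + 35 − 24 = 11 weeks at the earliest and 24 + 40 − 24 = 40 weeks at the latest. No term birth falls inside follow-up. A pregnancy loss could occur before week 24, but the Pregnancy paragraph would already have ended that participant's evaluations.

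**How many pregnancies**

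The documents give neither the number of women of child-bearing potential nor a pregnancy rate. Assumed ranges: 10% to 30% of the 95 participants, and 1 to 5 pregnancies per 100 woman-years.

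Expected number = 95 × fraction × rate × years, where years = weeks × 7 / 365.25.

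- 24 weeks (0.460 years): low 95 × 0.10 × 0.01 × 0.460 = 0.04; high 95 × 0.30 × 0.05 × 0.460 = 0.66.
- 30 weeks (0.575 years): low 95 × 0.10 × 0.01 × 0.575 = 0.05; high 95 × 0.30 × 0.05 × 0.575 = 0.82.

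The high figures pair both upper assumptions. The count serves only to size the cost of the fix.

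**The case against.** The best defence is that the Pregnancy paragraph is a deliberate, specific exception to a general rule. Ending procedures in pregnancy is a legitimate choice, and the discontinuation criteria support ending participation. That much stands. But those criteria do not cancel the discontinuation visit, and Timing of Evaluations states no exception. The two sections still need one sentence to reconcile them.

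The defence also limits how far the point can be taken. A reader might infer more in three places.

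- **Conflict with intent to treat, or with toxicity management.** Statistical Considerations says "All subjects, regardless of whether they remain on study drug, will continue to be followed throughout the duration of the study", and after a Grade 4 toxicity "subjects will be taken off study drugs but will continue to be followed and undergo the evaluations as per schedule of events". Both rules concern participants who stop the drug. Pregnancy is a reason to stop the study, so these sections can be read together without contradiction. The direct conflict is with Timing of Evaluations alone.
- **No means at all of recording a birth defect.** This goes too far. The Pregnancy paragraph bars evaluations and tests, not reporting, and asks participants to tell staff promptly of a suspected pregnancy. The adverse event definition begins with conditions arising during or after exposure, although it later refers to the follow-up period. The monitoring plan requires events above Grade 2 that are possibly related to participation to be reported to the IRB, with no end date. A late defect could be reported if someone learned of it. What is missing is any described step to find out. The consent pages were removed, and they might contain such a step.
- **Substantial loss of trial data.** The discontinuation visit yields one set of values. For a pregnancy found at week 6, it would not replace the scheduled week 12 and week 24 measurements. Values taken during pregnancy would also be of limited use for the biomarker endpoints.

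**Conclusion.** The point holds as a minor one. The Pregnancy paragraph and Timing of Evaluations give opposite instructions on the discontinuation visit, and no visible section describes active follow-up of pregnancy outcome despite the acknowledged fetal risk. Under the 38-week assumption, an on-study conception delivers 14 to 38 weeks after follow-up ends. Varying the time to term from 35 to 40 weeks widens this to 11 to 40 weeks and leaves the conclusion unchanged.

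About 0 to 1 pregnancies are expected, on assumed inputs. The gain is in safety data and clear instructions. The effect on the co-primary analyses is negligible, and no sample size, power or significance level changes. The second part rests on the visible text only.

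**What to change.** 1. In the Pregnancy paragraph, stop study drug when pregnancy is found, but carry out the single discontinuation visit from Timing of Evaluations. Limit it to assessments that are safe in pregnancy, obtain the participant's agreement, and flag the values as taken during pregnancy.
2. Add a limited exception to Intervention and Duration, Post-study Follow-up and Transition of Care, and the SAE and reporting sections. For conceptions on study or within 6 weeks of the last dose, record the pregnancy outcome by chart review or contact, with agreement, and report any birth defect as an SAE even after week 24.

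The cost is protocol and consent wording, plus one visit (already defined) and one chart review or contact per pregnancy. Chart review should often be feasible, because the Recruitment plans section says participants come mainly from the investigator's own practice.
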